5.4 Data Handling Conventions

5.4.1 Missing or Incomplete Date for Last Dose of Study Drug

In the Safety Analysis Set, if the last dose date of study drug is missing for a subject who completed or early terminated from the study, then the missing last dose date of study drug will be imputed using the last expected dosing date or EOT/ET date, whichever occurs earlier. The last expected dosing date will be calculated as the last drug dispense date plus the expected dosing interval days. For the incomplete last dose date of the study drug, the imputation algorithms will be detailed in the analysis dataset specification document. The missing or incomplete dates will be displayed in the data listings as reported on the eCRF rather than the imputed dates.

For the data summarization before final database lock, if a subject is still ongoing, then this subject's last dose date will be imputed using the database extract date.

5.4.2 Missing or Incomplete Dates for Concomitant or Post-Treatment Medications

Missing or incomplete medication start or end dates will be imputed for the purpose of determining whether the medications are taken concomitantly (see [Section 11](#) for definition). When the chronological order of medication use relative to the study drug treatment period is unclear due to missing or incomplete date(s), the medication will be considered as concomitant. The imputation algorithms will be detailed in the analysis dataset specification document. The missing or incomplete dates will be displayed in the data listings as reported on the eCRF rather than the imputed dates.

5.4.3 Missing or Incomplete Dates for Adverse Events

Missing or incomplete adverse event (AE) start dates will be imputed for the purpose of determining whether the AEs are treatment-emergent (see [Section 14.1](#) for definition). When the chronological order of an AE onset relative to the study drug treatment period is unclear due to missing or incomplete date(s), the AE will be considered as treatment-emergent. The imputation algorithms will be detailed in the analysis dataset specification document. The missing or incomplete dates will be displayed in the data listings as reported on the eCRF rather than the imputed dates.

5.4.4 Missing Severity Assessment for Adverse Events

If the severity is missing for a treatment-emergent AE, a severity of "Severe" will be assigned. The imputed values for severity assessment will be used for incidence summaries, and the actual values will be presented in data listings.

5.4.5 Missing Relationship to Study Drug for Adverse Events

If the relationship to study drug is missing for a treatment-emergent AE, a causality of “Related” will be assigned. The imputed values for relationship to study drug will be used for incidence summaries, and the actual values will be presented in data listings.

5.4.6 Character Values of Clinical Laboratory Variables

If the reported value of a clinical laboratory variable cannot be used in a summary due to, for example, a character string reported for a numeric variable, an appropriately determined coded value will be used in the summary. The coding algorithms will be detailed in the analysis dataset specification document. The actual values as reported in the database will be presented in data listings.

6 SUBJECT DISPOSITION

The number of sites that evaluated at least one subject for enrollment and number of subjects enrolled will be summarized by study (ACP-103-054 and ACP-103-059) and overall. Enrolled subjects are subjects who signed informed consent for Study ACP-103-055 and not recorded as “rollover failure” on eCRF.

For enrolled subjects, number and percentage of subjects in the Safety Analysis Set will be summarized. A listing will be provided displaying all subjects excluded from the Safety Analysis Set (if any), and will include reason(s) for exclusion.

The number and percentage of subjects in the Safety Analysis Set who completed the study or discontinued (all discontinued and by discontinuation reasons including the reasons due to COVID-19) will also be summarized. Summaries by study (ACP-103-054 and ACP-103-059) will also be presented.

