### **3 STUDY DESCRIPTION**

#### **3.1 Overview of Study Design**

This study will be a 52-week open-label extension study to evaluate the long-term safety and tolerability of pimavanserin in subjects with major depressive disorder and inadequate response to antidepressant treatment. Up to approximately 80 sites will participate in this study. The total duration of exposure to pimavanserin may be greater than 52 weeks (e.g., up to 58 weeks) as subjects may have been treated with pimavanserin in the antecedent studies, ACP-103-054 and ACP-103-059. The duration of participation for individual study subjects will be up to approximately 56 weeks.

The study will have two periods ([Figure S-1](#)):

- Open-label treatment period (52 weeks)
- Safety follow-up period (at least 30 days)

The end of treatment (EOT) visit for the antecedent study, Study ACP-103-054 or Study ACP-103-059, is the Baseline visit for the present study.

Subject consent for the present study must be obtained prior to the final procedures being performed at the antecedent study's (ACP-103-054 or ACP-103-059) end of treatment (EOT) visit. Data from the EOT procedures of Studies ACP-103-054 and ACP-103-059 will be carried over to the ACP-103-055 study to be included as baseline information for the present study and this visit will be considered Baseline (Visit 1).

The study completion date (or when a subject is considered to have completed the study) is defined as the date the final subject, across all sites, completes their final protocol-defined assessment. Please note that this includes the safety follow-up visit/contact, whichever is later. Procedures for when a subject is lost to follow-up are provided in [Section 4.5](#).

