### **4.4 Subject or Study Discontinuation**

Subjects may be discontinued from the study for a number of reasons, including, but not limited to, those listed below:

- Adverse event
- Death
- Lack of efficacy
- Lost to follow-up (Section 4.5)
- Non-compliance with study drug
- Physician decision
- Pregnancy
- Protocol deviation
- Study terminated by Sponsor
- Use of prohibited medication
- Other

The Sponsor reserves the right to discontinue the study at any time for any reason. Such reasons may be any of, but not limited to, the following:

- Occurrence of AEs unknown to date in respect of their nature, severity, and duration or the unexpected incidence of known AEs
- Medical, ethical or business reasons affecting the continued performance of the study

Regulatory authorities also have the right to terminate the conduct of the study in their region for any reason.

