3 STUDY DESIGN

3.1 General Study Design

This study is an open-label extension study to evaluate the long-term safety and tolerability of pimavanserin in subjects with major depressive disorder and inadequate response to antidepressant treatment. This study will be conducted as a 52-week extension of Studies ACP-103-054, and -059.

Subjects who have completed Studies ACP-103-054, or -059, who continue to meet entry criteria, and who may continue to benefit from adjunctive pimavanserin treatment based on the Investigator's judgment will be included in this long-term extension study.

[figure not shown]
All subjects will receive pimavanserin once-daily dosing at 34 mg over 52 weeks of treatment. During the treatment period, clinic visits will be conducted at Baseline and Weeks 2, 4, 8, 12, 16, 28, 40, and 52 (EOT), or upon early termination (ET) from the study.

Study drug will be dispensed to the subject to take home at the Baseline visit and at Weeks 4, 8, 12, 16, 28, and 40. The subject will be instructed to take the first dose of study drug on the day after the Baseline visit. It is recommended that the subject should take the study drug at approximately the same time each day.

A 30-day safety follow-up telephone contact is to be completed for subjects who complete the treatment period of the study, as well as those who discontinue prematurely from the study.

Figure 1 illustrates the study design.

Figure 1 Schematic of Study Design

Abbreviation: QD=once daily

Note: The antecedent study is either Study ACP-103-054 or Study ACP-103-059.

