3.5 Determination of Sample Size

It is estimated that approximately 420 subjects from Study ACP-103-054 and Study ACP-103-059 will be eligible to enter this study. The sample size for this study is not based on statistical power, but will depend on the number of subjects who transition into this open-label extension study from the antecedent studies, Study ACP-103-054 and Study ACP-103-059.

ACP-103-054, -059 and -055 were stopped early; the estimated number of subjects will be less than originally estimated.

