3.6 Coronavirus Disease 2019

In March, 2020, the emerging coronavirus disease 2019 (COVID-19) pandemic resulted in implementation of urgent safety measures designed to ensure subject safety. Mechanisms to record information on the potential impact of the COVID-19 pandemic on data itself, as well as data collection and integrity, were implemented (as detailed in the “Guidance for Site Documentation and Data Management Querying of Data Impacted by COVID-19” [GSD] in the Data Management Plan).

Screening and enrollment into studies ACP-103-054 and ACP-103-059 were closed and enrollment into ACP-103-055 was allowed to continue. The impact of COVID-19 on the statistical analysis is discussed in each of the relevant sections of this SAP.

Subjects who remained in this study who could not attend clinic visits were allowed to participate in remote visits via telephone or video, or site staff conducted the visit in a subject’s home. Sites were required to document details of all visits that are administered remotely.

Afterwards, ACP-103-055 was stopped early and the remaining subjects were discontinued in the study.

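### After the sponsor's early stop, the crude completion and discontinuation percentages in SAP section 6 cannot be read as 52-week figures, and a follow-up-adjusted summary is a cheap addition

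*SAP*

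**What the plan says.** Planned treatment is one year for everyone. SAP 3.1 states: "All subjects will receive pimavanserin once-daily dosing at 34 mg over 52 weeks of treatment".

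The SAP knows that this did not happen. Section 3.5 says: "ACP-103-054, -059 and -055 were stopped early; the estimated number of subjects will be less than originally estimated". Section 3.6, after describing the March 2020 pandemic measures, says that "enrollment into ACP-103-055 was allowed to continue", and then: "Afterwards, ACP-103-055 was stopped early and the remaining subjects were discontinued in the study".

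SAP 6 plans to summarize "The number and percentage of subjects in the Safety Analysis Set who completed the study or discontinued", with the breakdown described as "all discontinued and by discontinuation reasons including the reasons due to COVID-19". COVID-19 is the only reason it singles out. Protocol 4.4 lists "Study terminated by Sponsor" among the reasons for discontinuation, separately from adverse event and lack of efficacy.

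Neither document plans a time-to-discontinuation summary, a censoring rule at the stop, or a denominator limited to subjects who could have reached Week 52. The SAP does not define a completer. Protocol 3.1 runs the subject-level and study-level ideas together ("or when a subject is considered to have completed the study) is defined as the date the final subject, across all sites") and gives no Week 52 criterion. SAP 19 records no changes to the analyses in the protocol.

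**The concern.** A subject still on treatment when the sponsor closed the study can only be counted as discontinued. That lowers the completion percentage and raises total discontinuation for a reason unrelated to how the drug was tolerated.

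The effect on the other rows is less visible. A subject stopped at Week 30 had 30 weeks in which to leave for an adverse event or lack of efficacy, but counts fully in the denominator for those reasons. Each such percentage is therefore lower than its 52-week value, and the table does not hold what is needed to undo this.

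The primary objective is long-term safety and tolerability, and the study has no control arm and no hypothesis tests. Readers will compare these descriptive retention figures with those of other one-year extension studies, most of which they will assume had full follow-up.

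**Working it through.** **What the documents fix.** The SAP is version 1.0, dated 11 February 2021 (Appendix B). Week 52 is 364 days after Baseline, and 11 February 2021 minus 364 days is 13 February 2020. Any subject with Baseline after 13 February 2020 could not have reached Week 52 even by the SAP date. The stop is reported in the past tense, so the true cut-off for Baseline is that date or earlier. How many subjects this affects is not stated.

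**No figure to reproduce.** The 420 subjects in SAP 3.5 are a rollover estimate, with no assumed dropout or completion rate. The rest is illustration.

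**Illustration 1.** Assumptions, none from the documents:
- 52-week discontinuation for non-sponsor reasons is 30% under full follow-up, at a constant hazard: λ = −ln(0.70)/52 = 0.00686 per week.
- A share *s* of subjects has potential follow-up cut to a time uniform between Weeks 20 and 52.

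Among the cut subjects, the mean probability of still being on treatment at the cut is
[exp(−20λ) − exp(−52λ)] / (32λ) = (0.8718 − 0.7000)/0.2195 = 0.783,
so the mean probability of having already left is 0.217.

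The planned table then shows:
- completed = (1 − s) × 0.70
- non-sponsor discontinuation = (1 − s) × 0.30 + s × 0.217
- sponsor termination = s × 0.783

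| s | Completed | Non-sponsor discontinuation | Sponsor termination | All discontinued |
|---|---|---|---|---|
| 0 | 70.0% | 30.0% | 0% | 30.0% |
| 0.15 | 59.5% | 28.8% | 11.7% | 40.5% |
| 0.25 | 52.5% | 27.9% | 19.6% | 47.5% |
| 0.40 | 42.0% | 26.7% | 31.3% | 58.0% |

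Here *s* is the share with shortened potential follow-up. It is not the share recorded as sponsor-terminated, because some of these subjects leave earlier for other reasons.

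**Illustration 2 (heavier truncation, reasons separated).** Assume net 52-week risks of 10% for adverse events and 25% for other reasons, with constant hazards. A share *f* has follow-up cut uniformly over Weeks 0 to 52. In units of one year, h_AE = −ln(0.90) = 0.105, h_other = −ln(0.75) = 0.288 and h = 0.393. Full-follow-up completion is exp(−h) = 67.5%. Adverse-event discontinuation is (0.105/0.393) × 32.5% = 8.7%. The mean probability of being on treatment at the cut is (1 − 0.675)/0.393 = 0.827.

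| f | Completed | Adverse-event discontinuation | Sponsor termination |
|---|---|---|---|
| 0 | 67.5% | 8.7% | 0% |
| 0.25 | 50.6% | 7.7% | 20.7% |
| 0.50 | 33.8% | 6.7% | 41.3% |
| 0.75 | 16.9% | 5.7% | 62.0% |

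In both cases completion falls in proportion to the share cut, and the reason-specific rows fall by less, but always downward. Under these models, completed/(1 − s) returns the full-follow-up value. That is what a denominator limited to subjects able to reach Week 52 estimates.

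**The case against.** The strongest reply is that disposition is participant-flow accounting. The primary endpoint is treatment-emergent adverse events (Protocol 2.1.1). Neither document names disposition as an endpoint or calls the completion percentage a 52-week rate. No test or comparison depends on it. A reader might infer that the primary analysis is compromised, or that SAP 6 treats everyone as observed for 52 weeks. The documents support neither: a crude percentage of a stated number makes no claim about follow-up.

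A reader might also infer that the plan cannot tell sponsor-stopped subjects from the rest. That is too strong. Discontinuation is tabulated by reason, sponsor termination is a listed reason, and the row can be subtracted from the total. Exposure bands up to 52 weeks or more (SAP 10.1.1) will show that treatment was truncated. Discontinuations due to adverse events are also tabulated in SAP 14.1. Table specifications sit in a separate document (SAP 1) and may already settle the row labels.

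This reply limits the point but does not remove it. Subtracting the sponsor row corrects the total only for the administrative exits, and leaves the other rows based on shortened follow-up. The exposure bands are not linked to the reason for stopping, so they give no discontinuation risk. The SAP also never says which row the stopped subjects go into. The stop is described in the COVID-19 section, and COVID-19 is the only reason named in SAP 6, so coding could vary.

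**Conclusion.** The point holds as an improvement to a descriptive table. It does not show a wrong rule. SAP 6 was written with the early stop known, and its percentages cannot be read as 52-week completion or 52-week discontinuation by reason. No hypothesis test, sample size or primary endpoint is affected.

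The direction is certain for any subject whose follow-up was cut; the size is not known. Under Illustration 1, completion moves from 70% to between 59.5% and 42.0%. Non-sponsor discontinuation moves only from 30% to between 28.8% and 26.7%, about 1 to 3 points. Illustration 2 gives larger shifts because it assumes more and earlier truncation. All of these rest on assumed dropout rates, constant hazards and assumed shares and times of truncation.

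A reader might combine the SAP date with even accrual and present the resulting share of affected subjects as a lower bound. The documents give no accrual dates, no accrual pattern and no date for the last entry, so no such bound follows.

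**What to change.** In SAP 6, keep the planned table and state that subjects discontinued by the stop are reported in their own sponsor-termination row. State the stop date and what counts as completing, since the additions depend on both. Then add:

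- **(a)** Completion as a percentage of subjects whose planned Week 52 date fell on or before the stop date.
- **(b)** Cumulative incidence of discontinuation by reason (adverse event, lack of efficacy, other) from first open-label dose, treating the reasons as competing and censoring sponsor-terminated subjects at the stop. Give estimates and numbers at risk at Weeks 12, 28 and 52.

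Censoring at an administrative stop is reasonable if late entrants resemble early ones. Since late entry coincided with the pandemic, say so beside the table.

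The cost is a few sentences and one extra table from dose dates, discontinuation reasons and the stop date, with no new data collection. The downside is that late estimates may rest on few subjects, hence the numbers at risk.

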7 PROTOCOL DEVIATIONS

Protocol deviations that occurred during the extension study period will be reviewed periodically over the course of the study. The review process, definition of the deviation categories, and the classification of a deviation as major or minor are detailed in the Protocol Deviation Management Plan. Protocol deviations will also be assessed with respect to relationship to COVID-19.

For enrolled subjects, a summary of the number and percentage of subjects with major protocol deviations for each deviation category will be presented in three ways: all protocol deviations, COVID-19 related protocol deviations, and non COVID-19 related protocol deviations.

Two listings of major protocol deviations will be provided: all deviations and non COVID-19 related protocol deviations. A listing of all COVID-19 related protocol deviations including the major and the minor will be provided.

8 DEMOGRAPHICS AND OTHER BASELINE CHARACTERISTICS

Demographics and open-label Baseline characteristics will be summarized for the Safety Analysis Set using descriptive statistics. Summaries by study (ACP-103-054 and ACP-103-059) will also be presented. Variables include age, age group (18-40 years and >40 years), sex, primary race, ethnicity, height, weight, body mass index (BMI), antecedent study (ACP-103-054 and ACP-103-059), Baseline HAMD-17 total score, Baseline HAMD-17 total score <24 and ≥ 24 , Baseline CGI-S, Baseline SDS mean score, Baseline CSFQ-14 total score, Baseline KSS score, and antidepressant (SSRI and SNRI).

Race will also be categorized by White vs. Non-White. The eCRF reported age reflects a subject's age at the open-label Baseline visit date. Baseline CGI-S will be summarized as both a continuous variable and a categorical variable.

Depression history will be summarized for Safety Analysis Set using descriptive statistics. Variables include:

- Age at first onset of depression symptoms (years)
- Age at MDD diagnosis (years)
- Number of depression episodes during the subject's lifetime
 - Summary statistics for both the continuous variable and the categorical variable (1 to 5 and ≥ 6)
- Number of hospitalizations for depression during the subject's lifetime
 - Summary statistics for both the continuous variable and the categorical variable (0; 1 to 5; and ≥ 6)
- Duration of the current episode of depression (months relative to the open-label Baseline visit date)

Depression history as described above, date of last hospitalization (if number of hospitalizations is greater than 0), and onset date for the current episode of depression will also be presented in a data listing.

9 MEDICAL HISTORY

Medical history data will be coded using Medical Dictionary for Regulatory activities (MedDRA) version 23.0. The subject incidence will be summarized for each system organ class (SOC) and preferred term for the Safety Analysis Set. A subject will be counted only once per SOC or per preferred term for the summary.

A listing of the SOC, preferred term, body system, verbatim term for the medical history condition/event, start and stop dates (when available), and an indicator for whether or not the condition is ongoing will be provided.

10 EXTENT OF EXPOSURE AND TREATMENT COMPLIANCE

Summaries of exposure and compliance to study drug will be provided for the Safety Analysis Set.

10.1 Exposure to Study Drug

10.1.1 Exposure to Open-label Pimavanserin

For each subject, the duration of exposure to open-label pimavanserin (open-label last dose date – open-label first dose date + 1) will be calculated and summarized. The number and percentage of subjects within each of the following exposure levels in terms of duration of exposure will also be tabulated: <2 week (1 to 13 days), 2 to <4 weeks (14 to 27 days), 4 to <8 weeks (28 to 55 days), 8 to <12 weeks (56 to 83 days), 12 to <16 weeks (84 to 111 days), 16 to <28 weeks (112 to 195 days), 28 to <40 weeks (196 to 279 days), 40 to <52 weeks (280 to 363 days), ≥52 weeks (≥364 days).

In addition, the maximum dose in the open-label period, final dose in open-label period, and the mean daily dose during open-label period will be determined for each subject and summarized. The mean daily dose will be calculated as the number of pimavanserin tablets taken in the open label period multiplied by 17 (mg) divided by the duration of total exposure in the open-label period in days.

10.1.2 Total Exposure to Pimavanserin Across the Double-blind and Open-label Periods

For subjects who received pimavanserin in the antecedent studies, the total duration of exposure (in days) to pimavanserin will be calculated as the sum of the exposure durations in the double-blind and open-label periods:

$$[(\text{date of last double-blind dose}) - (\text{date of first double-blind dose}) + 1] + [(\text{date of last open-label dose}) - (\text{date of first open-label dose}) + 1].$$

In case that a subject whose last dose date in the antecedent study is equal the first dose date in the extension study, the total duration of exposure (in days) to pimavanserin will be the exposure durations in the double-blind and open-label periods minus one (i.e. the above formula minus one). For subjects who received placebo in the antecedent studies, the total duration of exposure to pimavanserin across the double-blind and open-label periods will be the same as the values calculated for the open-label study period alone. Duration of total exposure across the double-blind and open-label periods will be summarized descriptively.

Duration of total exposure will also be tabulated as a categorical variable: <2 week (1 to 13 days), 2 to <4 weeks (14 to 27 days), 4 to <8 weeks (28 to 55 days), 8 to <12 weeks (56 to 83 days), 12 to <16 weeks (84 to 111 days), 16 to <28 weeks (112 to 195 days), 28 to <40 weeks (196 to 279 days), 40 to <52 weeks (280 to 363 days), 52 to <54 weeks (364 to 377 days), 54 to <56 weeks (378 to 391 days), 56 to <57 weeks (392 to 398 days), and ≥ 57 weeks (≥ 399 days).

In addition, the maximum dose across the double-blind and open-label periods and the mean daily dose across the double-blind and open-label periods will be determined for each subject and summarized. The mean daily dose will be calculated as the number of pimavanserin tablets taken across the double-blind and open-label periods multiplied by 17 (mg) divided by the duration of total exposure across the double-blind and open-label periods in days.

